Washing blood products prior to transfusion has been shown to reduce inflammatory markers in pediatric cardiac surgery patients²¹ and improve survival in patients with acute leukemia²² However, widespread adoption of this practice has been limited by ongoing equipoise regarding its clinical impact as well as the logistical limitations of washing RBCs in the blood bank prior to transfusion.⁸ Our preliminary data demonstrate that: **A** we can predict which patients will receive RBC transfusions, thereby facilitating the targeted enrollment of a high-risk cohort, and **B** we can effectively remove BRMs from allogeneic LR-RBC units with a practical, point-of-care, Autotransfusion device. Therefore, to demonstrate the safety, efficacy, feasibility and clinical impact of this approach, we propose the following specific aims and testable hypotheses.

AIM 1: *To determine the feasibility, safety, and efficacy of point-of-care RBC washing using the Continuous Autotransfusion System (CATS) in adult cardiac surgery patients receiving allogeneic LR-RBC transfusion.*

Aim 1a - We hypothesize that point-of-care washing of allogeneic LR-RBCs will be feasible in the time-sensitive environment of cardiac surgery with minimal or no protocol violations.

Aim 1b - We hypothesize that when compared to standard-issue allogeneic LR-RBCs, washed allogeneic LR-RBCs will be associated with a comparable rise in hemoglobin concentration and will not be associated with evidence of increased hemolysis (CFH, haptoglobin) or acute kidney injury in the recipient.

Aim 1c - We hypothesize that RBC washing will reduce TRALI (neutral lipids, sCD40L, CCL5) and TACO (RBC-MPs, CFH) related BRMs in the RBC unit by greater than 80%.

AIM 2: *To demonstrate the extent to which point-of-care washing of allogeneic LR-RBCs impacts the recipient response to RBC transfusion when compared to standard-issue allogeneic LR-RBCs.*

Aim 2a - We hypothesize that RBC washing will reduce post-transfusion concentrations of validated lung injury-associated biomarkers (IL-6, IL-8, vWF, ICAM-1, RAGE, SP-D, PAI-1) in the transfusion recipient.

Aim 2b - We hypothesize that RBC washing will mitigate adverse physiologic consequences of RBC transfusion that have been associated with TACO (elevated mean arterial pressure, systemic vascular resistance, and pulmonary capillary wedge pressure).

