These algorithms accurately identified TRALI cases with a sensitivity and specificity of 83.9% (95% confidence interval [CI], 74.4%-90.4%) and 89.7% (95% CI, 80.3%-95.2%), respectively. For TACO, the sensitivity and specificity were 86.5% (95% CI, 73.6%- 94.0%) and 92.3% (95% CI, 83.4%-96.8%), respectively. Notably, of true-positive cases identified using the screening algorithms (TRALI/transfused ALI, n = 78; TACO, n = 45), only 11 (14.1%) and five (11.1%) were reported to the blood bank by clinical service, respectively.

The Continuous AutoTransfusion System (CATS) can eliminate potentially dangerous BRMs from stored allogeneic RBCs: In addition to previous work demonstrating effective elimination of protein⁸, CFH⁸, and RBC microaggregates¹⁰, our preliminary data suggest effective elimination of additional BRMs as well. Specifically, 4 LR-RBC units were washed with the CATS device using a 4:1 dilution process as previously described.⁸ RBC-MPs, sCD40L, and CCL5 concentrations were assessed before and after the washing procedures. The reduction in microparticle concentration exceeded 80 % in all cases evaluated with a median (IQR) percent change of 92.2% (82.2% – 98.7%). Similar reductions were noted in CCL5 for all 4 units evaluated and in sCD40L for 2 of the 4 units. The remaining two units had low levels of sCD40L in the pre-wash sample. A representative pre-, post-wash sample evaluating RBC-derived

microparticle counts is presented in figure 4.

Biomarkers as intermediate outcomes for clinical lung injury (Grant #:K23HL112855-01): Our team has substantial experience in the study and use of biomarkers as intermediate surrogate outcomes for clinical lung injury. Our current K23 award (PI: [name]) specifically aims to evaluate the use of biomarkers to better understand the mechanisms underlying postoperative acute respiratory distress syndrome (ARDS). As preliminary data for the present proposal, we evaluated the biomarker profiles of 12 patients who developed ARDS following cardiovascular surgery with 12 matched controls who did not. As can be seen in Figure 4, differing biomarker profiles were noted in those who developed postoperative ARDS when compared to those who did not. In light of this preliminary data, we have refined our biomarker panel in this A1 resubmission to include IL-6, IL-8, PAI-1, and RAGE as the intermediate outcomes for Aims 2a/c of this proposal.

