Specific Aim 1: The **primary feasibility outcome in aim 1a** will be the number and proportion of "off-protocol" allogeneic RBC transfusions administered during the study intervention period (day of surgery). A secondary feasibility outcome will be the time required for the RBC washing procedures (defined as the time from determination of RBC need by the clinical team to time of delivery of the RBC unit to the clinical team). This time will be computed for all patients and all transfusions during the study intervention period (in both the intervention and control cohorts). The **primary safety outcome in (aim 1b) include** the change in the RBC recipient's Hb concentration from pre- to post-transfusion as well as the concentration of CFH and haptoglobin following RBC transfusion. To assess the primary safety outcomes, samples for total Hb, CFH, and haptoglobin will be obtained prior to transfusion, as soon as possible after the first transfusion, but no later than 30 minutes following the first intervention/control RBC transfusion, as well as 6 hours (+/- 30 minutes) and 18 hours (+ / - 30 minutes) from the end of first study RBC transfusion for all study participants. We will also assess for clinical evidence of acute kidney injury throughout the hospitalization. Safety labs will also be drawn anytime on study day #5 if the patient is still in the hospital. The **primary efficacy outcome in aim 1c** will be the change in the concentration of neutral lipids [arachidonic acid, 5-hydroxyeicosatetraenoic acid (HETE), 12-HETE, 15-HETE], sCD40L, CCL5/RANTES, RBC-MPs, and CFH in the RBC component from the pre- to the post-wash phase. These data will allow us to calculate the CATS-related elimination rates for these BRMs, which have previously been associated with transfusion-related respiratory dysfunction and hemodynamic alterations. To balance assay costs while ensuring the scientific success of aim 1c, pre- and post-wash samples will be obtained/analyzed for the first 75 washed RBC units. If efficacy is not clearly established, we will continue to obtain both pre- and post-wash samples for 75 additional units.

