Statistical Considerations (prepared in collaboration with our statistical: Aim 1 is centered on the clinical and technical feasibility of on-demand RBC washing (hypothesis 1a). Feasibility is defined as the administration of protocol RBCs instead of "off-protocol" standard-issue RBCs. Simon's two-stage design will be used to determine if the protocol needs to be modified to prepare RBCs prior to the surgical procedure. The null hypothesis rate for feasibility is $p \leq 0.75$ versus the alternative that $p \geq 0.90$, where p is the probability of successfully preparing and administering the intervention RBCs. Stage 1 of the design will examine the first 16 cases randomized to RBC washing. If 12 or fewer transfusions were deemed "feasible", the protocol will be modified to pre-wash RBCs (see limitations). If 13 or more are feasible, an additional 32 cases will be evaluated. Should 39 or fewer (of the 48 studied) not be feasible, the protocol will be modified to pre-wash. If 40 or more cases meet the feasibility definition, the remainder of the study will go as originally planned. (Sample size/ design calculations details: PASS 2008, alpha=0.10, beta=0.10, Optimal design). The safety endpoint for aim 1 is the change in hemoglobin level (hypothesis 1b). The change in hemoglobin after the first transfused unit will be used as the primary safety measure. Wilcoxon rank sum tests will be used to compare change in hemoglobin levels between randomized groups. The change in concentrations of soluble BRMs (e.g.

neutral lipids; hypothesis 1c) will be assessed using paired t-tests. There is > 80% power to detect a 0.4 SD difference pre- to post-washing with 78 washed RBC products. Should there be fewer (due to feasibility), power will decrease. However, the magnitude of differences observed in preliminary data (92% reduction, Figure 4) is many times larger than an effect size of 0.4. Therefore, power for this hypothesis should not be a concern.

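### Aim 1c hypothesizes a fall of more than 80% in each BRM, but the planned paired t-test can show only that some fall occurred, and low pre-wash sCD40L has no handling rule

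*Combined protocol and SAP*

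**What the plan says.** - **Hypothesis (Specific Aims, Aim 1c).** Washing is to reduce the TRALI and TACO "related BRMs in the RBC unit by greater than 80" percent. The BRMs named are neutral lipids, sCD40L, CCL5, RBC microparticles and cell-free hemoglobin (CFH).
- **Outcome (Outcome Measures, Specific Aim 1).** The primary efficacy outcome is the pre- to post-wash change in concentration. The section adds: "These data will allow us to calculate the CATS-related elimination rates for these BRMs". It gives no formula for the rate.
- **Test (Statistical Considerations, Aim 1).** "neutral lipids; hypothesis 1c) will be assessed using paired t-tests". No log or ratio scale and no null value other than zero is stated.
- **Power (same section).** "There is > 80% power to detect a 0.4 SD difference pre- to post-washing with 78 washed RBC products". The section adds that the pilot reduction of 92% makes power no concern.
- **Number of units (Outcome Measures, Specific Aim 1).** "pre- and post-wash samples will be obtained/analyzed for the first 75 washed RBC units", and then: "If efficacy is not clearly established, we will continue to obtain both pre- and post-wash samples for 75 additional units". No criterion defines clear efficacy.
- **Pilot (preliminary data on the CATS device).** Four units were washed. Microparticles fell by more than 80% in every unit, with a median of 92.2%. CCL5 fell similarly in all four and sCD40L in two. On the others: "The remaining two units had low levels of sCD40L in the pre-wash sample".
- **Protocol Addendum.** The 75-unit analysis is complete. Microparticles and cytokines decreased, CFH increased, and the wash is described as effective in removing BRMs. No percentage is given. The 6 ml pre-wash sample is no longer collected.

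**The concern.** The hypothesis is about a ratio with a threshold; the test is about an absolute difference from zero. A wash that removes a fifth of a BRM and one that removes nine tenths can both give a clearly significant paired t-test. The result decides whether 75 more units are sampled, and it underlies the addendum's statement that the wash works. A statement that concentrations decreased is all that such a test can supply.

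Elimination rates could fill the gap, but the plan does not say how to compute them or how to treat units that start near the assay limit. The pilot had already met low pre-wash sCD40L, and it reported the similar reduction only for the other two units.

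**Working it through.** **1. The plan's own figure.** Exact paired t-test power (noncentral t) for a 0.4 SD difference and 78 units is 96.8% at two-sided alpha 0.10 and 93.7% at 0.05. With the 75 planned units it is 96.3% and 92.8%. Alpha 0.10 is stated for Aim 2a and not restated for Aim 1c. The claim of more than 80% is therefore true as a lower bound. It looks carried over from the two-group calculation for Aim 2a: n = 2 × (1.645 + 0.842)² / 0.4² = 77.3, so 78 per group, power 80.3%. In either case the power is against zero, not against an 80% fall.

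**2. Why the t-test does not address 80%.** Suppose the wash removes the same fraction f from every unit. Each difference is then f × pre. The standardized effect is f × mean(pre) / [f × SD(pre)] = mean(pre) / SD(pre). The fraction cancels, so the t statistic is the same for a 10% and a 92% fall. Variation in the wash effect between units breaks this exact cancellation but does not turn the test into one of the threshold.

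**3. Size, by simulation.** The documents give no spreads, so these are assumed. With n = 75, two-sided alpha 0.10 and no assay floor:

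| True fall | Paired t-test against zero rejects (log SD of pre-wash 0.5, of wash ratio 0.3) | Log-ratio test against an 80% fall rejects (one-sided 0.05, same spreads) |
|---|---|---|
| 10% | 48% | 0% |
| 20% | 99.5% | 0% |
| 50% | 100% | 0% |
| 70% | 100% | 0% |
| 80% | 100% | 5% |
| 92% | 100% | about 100% |

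With wider pre-wash spread (log SD 1.0-1.5), the paired t-test rejects in about 78-94% of trials at a true 20% fall and in at least 99% at 50%. More variable wash ratios would lower the figure at 20%.

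**4. Assay floor for sCD40L.** Let L be the lower limit. If post-wash non-detects are set to L, the largest observable fall is 1 - L/pre:

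- pre = 1.5 L: 33%
- pre = 3 L: 67%
- pre = 5 L: 80%

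With L/2 substituted, the same three levels give 67%, 83% and 90%, and an 80% fall needs pre of at least 2.5 L. The plan states no substitution rule, so both are assumptions.

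Simulation with a true 90% fall in every unit, log-normal pre-wash values (log SD 1.0-1.5):

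| Pre-wash median | Non-detects set to | Mean elimination | Median elimination | Units above 80% |
|---|---|---|---|---|
| 5 L | L | 64-70% | 80% | 50% |
| 5 L | L/2 | 73-81% | 90% | 68-76% |
| 20 L | L or L/2 | 83-90% | - | - |

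In the 5 L runs the ratio of means is 85-89%.

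A second set used a true median fall of 92%, with low units at 1.5-3 L and the rest at 30 L. Mean elimination was 91.5-91.8% with no low units, 77-89% with a quarter low, and 62-86% with half low. With half low, the ratio of means stayed at 89-91%, and restricting to units with pre of at least 5 L gave 90.5-91.8%. The paired t-test rejected in 100% of these runs, floor or not.

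**5. Share of low units.** The pilot share is 2/4, with exact 95% interval 7% to 93%.

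**The case against.** Aim 1c is a laboratory aim on blood units, the trial is sized on Aim 2a, and the 75-unit analysis is already done. The pilot falls were large, and the pilot summarized by a median, which the floor barely moves when L/2 is substituted. In the simulations with a large true fall, the floor lowers the elimination figure, so any bias works against the wash. All of this stands, and it limits the assay-limit part of the point.

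A reader might go further and infer that half the units are too low in sCD40L to show an 80% fall, and that the elimination figure therefore reflects the assay floor and not the wash. The documents do not support that:

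- They say only that two of four units were low. They give no concentration, assay limit or post-wash value, and four units cannot fix a rate for the trial.
- The one elimination figure reported, 92.2%, is for microparticles, and CCL5 fell similarly in all four units. Low pre-wash levels are reported for sCD40L only.
- A floor does not explain the rise in CFH.
- No substitution rule is written, and no scale is stated for the t-test. Raw concentrations are the plain reading, not a stated choice.
- Mean elimination as low as 64-70% needs low assumed pre-wash levels, full-limit substitution and a per-unit arithmetic mean together.

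None of this answers the main point: a test against zero does not test a fall of more than 80%.

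**Conclusion.** The mismatch between hypothesis and test is established from the text and, in the constant-fraction case, by algebra. Its size, about 78-94% rejection at a true 20% fall, rests on assumed spreads. A significant decrease, which is all the addendum reports, does not show that the 80% hypothesis was met. Nor does it show that the hypothesis failed for the BRMs that decreased; the question is left unanswered for them.

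The assay-limit problem is a secondary gap, documented for sCD40L alone. Its direction is probably downward, and its size cannot be determined: with a true 90% fall, the assumed scenarios give mean elimination from about 64% to 90%, and a median or ratio of means is much less affected.

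**What to change.** As a supplementary analysis of the existing 75 units:

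1. For each BRM, analyze log(post/pre). Report the geometric mean elimination with its confidence interval and compare it with the 80% threshold, a ratio of 0.20.
2. State each assay's lower limit. Where values fall below it, expected mainly for sCD40L, treat them as left-censored in a likelihood analysis. Count separately any pair with both values below the limit, since it says almost nothing about the ratio.
3. Base the share of units above 80% on units with a pre-wash value of at least 5 times the limit, and give the number evaluable. At that level a non-detect after washing implies post < L ≤ pre/5, so a fall of more than 80% whatever substitution is used.
4. Give the elimination-rate formula, and label the analysis post hoc because Aim 1c is already reported as complete.

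The cost is re-analysis of data in hand. The downside is fewer informative sCD40L units: about 37 of 75 if half were below 5 times the limit (0.5 × 75 = 37.5), but the pilot interval allows anything from about 5 (0.07 × 75) to 70 (0.93 × 75). A post hoc result also carries less weight than a prespecified one.

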Figure 4. RBC microparticle counts before (left) and after (right) washing with the CATS.

[figure not shown]
[figure not shown]
[figure not shown]

Figure 4. Lung injury biomarkers in patients who do and do not develop ARDS.

PHASE I/II CLINICAL TRIAL EVALUATING POINT-OF-CARE RBC WASHING TO PREVENT RBC-ASSOCIATED RESPIRATORY COMPLICATIONS FOLLOWING CARDIAC SURGERY

Study population: Study procedures are summarized in Figure 5. We will enroll a total 154 patients receiving at least one RBC transfusion on the operative day. We anticipate this will require randomizing up to **190 patients** in this trial (95 per group). Adult patients (age ≥ 18) who are planned to undergo cardiac surgery at one of the two participating institutions and who have a predicted RBC transfusion requirement of ≥ 4 units will be screened for the exclusion criteria outlined in Table 4. Predicted RBC transfusion requirements will be determined utilizing a recently published large-volume blood transfusion (LVBT) prediction model (>4 units of RBC).⁷³ A cut off of 4 predicted units of RBC administration was chosen because: 1) this transfusion volume has been associated with increased risk of pulmonary complications following cardiac surgery⁵⁸; 2) we have previously identified this transfusion volume as a common “dose” in patients who experience TRALI and/or TACO^{28, 39,42}; and 3) this threshold would still identify a sizable cardiac surgery population, ensuring study feasibility.

Study procedures:

Screening: Study coordinators will screen all adult (age ≥ 18) patients who are scheduled to undergo coronary artery bypass graft surgery with or without valve repair/replacement, complex cardiac valve surgery, pericardial resection, and/or ascending aortic surgery in one of the two participating institutions. Eligible patients with a predicted transfusion requirement of 4 or more units will be approached before their elective surgical procedure by a study coordinator for consent. After confirming the patient's inclusion and exclusion criteria, the study coordinator at the respective institution will obtain informed consent and assign a study ID number to the study participant. Screening logs will be maintained at each site to allow generation of a CONSORT diagram.

Table 4. Exclusion criteria.

Exclusion Criteria	Justification
• Emergency surgery	Inability to randomize/perform study procedures
• IgA deficiency	Not ethical to randomize to standard issue RBCs

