Study intervention: The intervention in this investigation will be implemented for all allogeneic RBCs administered on the day of surgery (intraoperative and postoperatively on Study Day 1). The decision to administer an allogeneic RBC transfusion will be left to the responsible clinical service and will not be prespecified in the study protocol. We have elected to leave this decision to the clinical service for the following reasons: 1) the target population frequently experiences major acute blood loss; in these circumstances, typical measures assessing the need for RBC transfusion (e.g. Hb) are often associated with unacceptable time delays and frequently do not reflect true red blood cell mass nor need for RBC transfusion; 2) this design facilitates a more meaningful understanding of the feasibility of RBC washing in clinical practice. Upon receiving an order for allogeneic RBC transfusion, the transfusion medicine service will prepare the RBC product according to the allocated treatment assignment (intervention versus control). Of note, all allogeneic RBC units at the two participating institutions undergo pre-storage leukocyte reduction.

Intervention cohort: For patients randomized to receive washed RBCs, all allogeneic RBCs **administered** on the day of surgery will be washed with the CATS device prior to transfusion. To account for the time

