The effects of storage duration will also be assessed. The mean age of the transfused blood products will be determined. This value will be used to test for effect modification (interaction with treatment). Specifically, the main effect of RBC age, its interaction action with treatment, time and the treatment-by-time interaction term will be used to determine if the biomarker trajectories are affected by RBC age. It is hypothesized that the washing protocol will attenuate the effects of age resulting in more uniform trajectories over the range of RBC age where as the unwashed RBC will show increases in biomarker values as RBC age increases.

Sample Size Considerations: The sample size for this clinical trial is based on the mechanistic outcomes detailed for Specific Aim 2a. Table 2 in Fremont et al. was used to provide estimates of the range of effect sizes for the biomarkers considered in this study.⁸⁰ Using an approximation of the standard deviation from the interquartile range ($SD \approx IRQ/1.35$), the median effect size was found to be 0.4. This magnitude of change would be relevant, and appropriate to power this study on. With equal allocation between the groups, the sample size for this study is estimated to be $n=78/group$ ($\alpha=0.10$, two-sided; see additional statistical considerations below). Actual power is expected to be higher on account of the repeated measures design. To allow for drop out and “non-feasible” cases, we plan to enroll and randomize patients until 154 patients have undergone surgery and had at least one transfusion on the operative day. We anticipate this may require randomizing up to 190 total patients. Any patients randomized and awaiting surgery when the 154th patient is achieved will also be included. The final sample size may be adjusted further based on the feasibility findings observed in the two-stage design.

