Aim 3 will utilize standard analytical measures for comparing randomized treatment groups with ITT. For data that may be skewed (e.g., length of ventilation, ICU stay), Wilcoxon rank sum tests will be used to compare groups. Serial measurements (oxygen saturation) will be analyzed using longitudinal summary statistics (e.g., AUC, mean value). It should be noted that the intermediate clinical outcomes are not being powered for in this study. Estimates of precision (confidence intervals) along with range of responses will be used to guide subsequent trial designs (e.g. a larger phase II/III trial with clinical outcomes as the primary outcome of interest).

Additional statistical considerations: Consistent with early phase clinical trials, we have selected a level of significance higher than the traditional 0.05. This will facilitate advancement of the technique should it prove feasible and demonstrates potential efficacy. It is noted that multiple testing may increase the overall family wise error rate, so further research, particularly with clinical events, will be needed to quantify clinical efficacy of the approach. Missing data is expected to be minimal during the course of the study given the close surveillance the surgical and ICU environment provides. Missing specimens may occur in the event of patient discharge, death or administrative issues. Initial analyses will be conducted under the assumption of MCAR/MAR (ignorable missing). Sensitivity analyses using multiple imputation and pattern mixture models will be used to assess the robustness of the model assumptions. The analysis of specific aim 2 proposes to use a modification of the ITT principle. Justification for this is that it is a mechanistic aim with blinded examiners. We are interested in quantifying the effects of washing as clearly (and perhaps ideally) this is an early phase trial. In Aim 3, the clinical outcomes will be assessed using the traditional ITT definition to provide a more realistic measure of the effect size for planning subsequent studies.

Protocol Addendum:

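### The Aim 1c paired t-tests treat 75 washed RBC units as independent although one patient can supply several, so standard errors are too small if changes correlate within patients

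*Combined protocol and SAP*

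**What the plan says.** Aim 1c hypothesises that washing lowers each listed BRM in the unit, CFH included, by more than 80%.

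- **Sample.** Under Outcome Measures, Specific Aim 1, "pre- and post-wash samples will be obtained/analyzed for the first 75 washed RBC units". If efficacy is not clear at that stage, "we will continue to obtain both pre- and post-wash samples for 75 additional units". The count is of units, not patients.
- **Test.** Under Statistical Considerations, the changes "will be assessed using paired t-tests". The power statement reads: "There is > 80% power to detect a 0.4 SD difference pre- to post-washing with 78 washed RBC products".
- **Source of the units.** The Study population section enrols patients "who have a predicted RBC transfusion requirement of ≥ 4 units". In the intervention cohort, all allogeneic RBCs given "on the day of surgery will be washed with the CATS device prior to transfusion", subject to the 23:30 ordering cut-off and the emergency off-protocol exception.
- **Handling of dependence.** Random effects are planned only for the recipient biomarkers of Aim 2. Table 4 excludes repeat enrolment of a patient because it would break independence, but nothing comparable is said about several units from one patient in Aim 1c.
- **Status.** The Protocol Addendum says the 75-unit analysis is complete: microparticles and cytokines fell, CFH rose, and the pre-wash 6 ml sample is no longer collected. It gives directions only, with no estimate, SD, p-value or interval.

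**The concern.** A paired t-test removes each unit's own level, because every unit is its own control. It does not remove correlation between the *changes* of units given to the same patient, and it counts each unit as a separate piece of information.

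There are credible reasons for some correlation. Site is always shared within a patient. Units issued for the same operation may have similar storage ages, and the Significance section says BRMs accumulate in storage. When most of a substance is removed, the absolute change is close to proportional to the pre-wash level, so similar storage ages would carry into similar changes. The 4:1 dilution is described as approximate, so wash set-up may also be shared.

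Three things depend on precision here: whether removal exceeds 80% rather than merely zero, whether efficacy was clear enough to forgo the second 75 units, and how well the unexpected CFH rise is known.

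**Working it through.** **Inputs from the documents.** 75 units (Outcome Measures, Specific Aim 1); 78 units, 0.4 SD and power above 80% (Statistical Considerations). Alpha 0.10 two-sided is stated for the Aim 2a sample size. I take it to apply here because Additional statistical considerations says "we have selected a level of significance higher than the traditional 0.05" without limiting this to one aim.

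**Inputs assumed.** Units per patient, m = 2 to 4; the mean is not given. Four is the predicted-need threshold, not an observed mean; at one site, 310 of 1,059 transfused patients (29%) in 2011 received 4 or more. The ICC of the changes within a patient is not given either; I use 0.1 to 0.5. Cluster sizes are taken as equal; unequal sizes would raise the design effect somewhat.

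**Step 1: the plan's own figure.** Power of a paired t-test at 0.4 SD with 78 independent units (noncentral t, 77 df) is 96.8% at two-sided alpha 0.10 and 93.7% at 0.05. With 75 units it is 96.3% and 92.8%. The claim of more than 80% is therefore true as a lower bound under independence. The same 78 with 0.4 SD gives 80.0% as a two-group comparison at alpha 0.10, which is the Aim 2a calculation, so the patients-per-arm figure appears to have been reused as a unit count.

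**Step 2: allow for nesting.**
- Design effect: DE = 1 + (m − 1) × ICC
- Effective n = 75 / DE
- Standard-error multiplier = √DE
- True error of a nominal 0.10 test = 2 × [1 − Φ(1.645 / √DE)]
- True coverage of a nominal 95% interval = 2 × Φ(1.96 / √DE) − 1
- Power at 0.4 SD and alpha 0.10: noncentral t with effective n and (patients − 1) df

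Example, m = 4 and ICC 0.5: DE = 1 + 3 × 0.5 = 2.5; effective n = 75 / 2.5 = 30; √2.5 = 1.58.

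| m (patients) | ICC | DE | Effective n | SE × | True error at 0.10 | True coverage at 95% | Power, 0.4 SD |
|---|---|---|---|---|---|---|---|
| any | 0 | 1.0 | 75 | 1.00 | 0.10 | 95% | about 96% |
| 2 (about 37) | 0.1 | 1.1 | 68 | 1.05 | 0.12 | 93.8% | 94.5% |
| 2 | 0.3 | 1.3 | 58 | 1.14 | 0.15 | 91.4% | 90.9% |
| 2 | 0.5 | 1.5 | 50 | 1.22 | 0.18 | 89.0% | 87.1% |
| 4 (about 19) | 0.1 | 1.3 | 58 | 1.14 | 0.15 | 91.4% | 89.9% |
| 4 | 0.2 | 1.6 | 47 | 1.26 | 0.19 | 87.9% | 83.8% |
| 4 | 0.3 | 1.9 | 39 | 1.38 | 0.23 | 84.5% | 78.0% |
| 4 | 0.5 | 2.5 | 30 | 1.58 | 0.30 | 78.5% | 67.8% |

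**Step 3: where it changes a conclusion.** For a change of 1 SD at m = 4 and ICC = 1, the worst case for that m (effective n about 19), power against zero is still 99.4% at alpha 0.10. A drop near the preliminary microparticle figure of 92.2% would therefore still be distinguished from no change.

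A judgement against 80% has less room, since the preliminary interquartile range starts at 82.2% and comes from four units. A result that just clears 80% with a nominal statistic of 1.96 would have a correct statistic of 1.96 / 1.14 = 1.72 at DE 1.3, and 1.96 / 1.58 = 1.24 at DE 2.5. The same multipliers apply to the CFH rise, whose size the documents do not give.

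**The case against.** The strongest reply is that the correlation is inferred and may be negligible. The documents do not say that one operator or one device set-up handles all of a patient's units. Units given during and after surgery may be washed hours apart, the device runs in a fixed wash mode, and similar storage age is only plausible. Operators, devices and sites are also shared across patients, so a patient term would not isolate their effects. The mean number of units per patient may be well below 4: some randomised patients are expected to receive none, and the unit sampling described for Aim 2c stops at the fourth unit. At m = 2 and ICC 0.1 to 0.3, the correction is only 5% to 14%. All of this stands. It makes the point conditional and bounds its size, but it does not justify assuming ICC = 0 without looking.

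A second reply is that large drops will be significant whatever the ICC. That also stands for tests against zero. It does not cover the 80% target or CFH. A paired t-test against zero does not test the 80% target anyway; that is a separate gap from clustering.

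A reader might infer that intervals already published for BRM removal and CFH are too narrow. The documents do not support this. No interval is planned for Aim 1c, the addendum reports none, and it does not say how the completed analysis was done.

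**Conclusion.** The point holds in conditional form. Units are nested in patients, and the planned test ignores this. If the changes are positively correlated within a patient, standard errors and p-values, and any intervals derived from them, are too small. For 2 to 4 units per patient and ICC 0.1 to 0.5, both assumed, standard errors should be about 5% to 58% larger; at ICC 0 there is no error.

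It does not follow that the reported fall in microparticles and cytokines is in doubt, or that the power statement fails for effects as large as those expected. At exactly 0.4 SD, power falls below 80% only towards the upper end of the range (m = 4 with ICC 0.3 or more). The consequence is confined to judging removal against 80%, including the decision on the second 75 units, and to the precision of the CFH rise. This is a worthwhile, inexpensive improvement and not a threat to the trial.

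**What to change.** 1. Report the number of patients, and of units per patient and site, behind the 75 units.
2. Re-run the completed Aim 1c analysis with standard errors clustered on patient, or with a mixed model for the change with a random patient intercept and a fixed site effect, at least as a sensitivity analysis. With perhaps 19 to 37 patients, use a small-sample correction. Give the estimate, interval and ICC for each BRM and for CFH. If the completed analysis already allowed for patient, saying so is enough.
3. Choose the scale for each BRM. A log ratio suits proportional removal but may be unstable where the pre-wash level is low, as for sCD40L in two of the four pilot units.
4. Add one sentence to the Aim 1 paragraph of Statistical Considerations naming the patient as the clustering unit.

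The cost is a re-analysis of existing data, with no new samples. The downside is wider intervals if the ICC is not near zero, up to about 58% in the assumed range. If the ICC proves near zero, the question is closed with data.
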